On the other hand, osteophytes formation at the entheseal regions of the joints in PsA is distinctive feature compared with RA (13). The formation of osteophytes is tightly regulated by anabolic pathways, which resembles the pathogenesis of new bone formation in ankylosing spondylitis (AS). Tumor necrosis factor (TNF) inhibition was unable to halt the structural progression in AS patients (14-16), it also lacked efficacy in stopping the progression of osteophytes in PsA patients (17). Inhibition of IL-17 by secukinumab was effective in the treatment of both AS (18) and PsA (12). Secukinumab also decreased the rate of radiographic joint damage regarding to erosion and joint space narrowing (12). However, it is unknown if it has any effect in the progression of osteophytes. In an animal model, although over-expression of IL-17 alone failed to induce entheseal and periosteal bone formation, inhibition of IL-17 leaded to significant reduction of such bone formation in an IL-23 overexpression model (19). Moreover, IL-17A accelerates bone formation by stimulating the proliferation and osteoblastic differentiation of mesenchymal progenitor cells after injury (20). It is worth exploring if secukinumab could prevent the progression of osteophytes in PsA patients.

Aims and hypotheses to be tested:

Hypothesis

IL-17 inhibition by secukinumab could lead to healing of existing erosion, and prevent progression of osteophytes, and resolution of dactylitis in PsA patients.

Aims

The aim of this randomized, double-blind, placebo-controlled study is to evaluate the protective effects of secukinumab on the healing of joint erosion and prevention of progression of osteophytes in PsA patients using HR-pQCT and US.

Objectives

Primary outcome

Difference in changes in the volume of erosions on metacarpophalangeal joints (MCP) 2-4 measured by HR-pQCT at 24 and 48 weeks between secukinumab and placebo group.

Secondary outcomes

- The percentage of erosions with healing determined using HR-pQCT on MCP 2-4 at 24 and 48 weeks including 1). A decrease in erosion volume of ≥0.4 mm³ from baseline, and 2). The presence of grade 2 osteosclerosis at the margin of erosion.
- 2) Changes in volume and width of erosion using HR-pQCT at 24 and 48 weeks;
- 3) Changes in the height of osteophytes using HR-pQCT at 24 and 48 weeks;
- Marginal osteosclerosis (semi-quantitative and quantitative) using HR-pQCT at 24 and 48 weeks;

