- 5) Changes in joint space volume using HR-pQCT at 24 and 48 weeks

Exploratory outcomes

- 1) Changes in US-parameters in dactylitis, enthesitis and synovitis at 24 and 48 weeks
- 2) Changes in van der Heijde-Sharp score on radiograph at 24 and 48 weeks.
- 3) Changes in patients-reported-outcomes (SF-36, Psoriatic Arthritis Impact of Disease (PsAID)) and functional disability (HAQ) at 24 and 48 weeks
- 4) Changes in biomarkers (Pro-C2, C-Col10, COMP, MCP-1, Dkk1 and sclerostin) at 24 and 48 weeks

Plan of Investigation:

Subjects 120 biologic DMARDs naïve PsA patients attending the outpatient clinic of the Prince of Wales Hospital (PWH), North District Hospital (NDH), Tai Po Hospital (TPH), Queen Elizabeth Hospital (QEH) and Tseung Kwan O Hospital (TKOH) who fulfilled the Classification Criteria for Psoriatic Arthritis (CASPAR), will be recruited. The main inclusion criteria are: 1) ≥18 years old; 2) without severe deformity in MCP joints (MCPJ) which would influence the longitudinal assessment of HR-pQCT; 3) with active disease, which is defined as three or more tender joints and three or more swollen joints, despite previous treatment with nonsteroidal anti-inflammatory drugs, disease-modifying antirheumatic drugs. These 120 patients will be screened for the presence of erosion at the head of MCPJ 2-4 using HRpQCT. The first 40 patients with erosion will be randomised in a 1:1 ratio to secukinumab (n=20) or placebo (n=20) group. Based on a study using high-resolution CT in 41 PsA patients, 41% of the patients had at least one erosion, and 90% of the erosions were in MCPs (5). The resolution of the highresolution CT is 0.4 mm, which is almost 5 folds lower than HR-pQCT (82 µm). Therefore, we estimated that over 1/3 of the PsA patients will have at least one erosion in MCPs. Thus, screening 120 patients using HR-pQCT should be adequate to recruit 40 patients with erosions on MCPJ 2-4.

All study procedures will be performed in PWH after recruitment from non-PWH site.

Randomisation will be performed using a computer-generated randomisation list provided by the hospital pharmacist, using a permuted blocks design with block sizes of 4 and 6. Allocation concealment will be ensured by the use of sequentially numbered, opaque, sealed envelopes. Treatment will be masked to patients and investigators.

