Erosion identification and measurement of the width and depth

Erosions are defined as sharply marginated bone lesions with juxta-articular localisation with a cortical break seen in at least two adjacent slices, which are often accompanied by loss of the adjacent trabecular bone. Erosions will be differentiated from physiological breaks indicating entry of blood vessels by the linear shape and occurrence on predilection sites. Pseudo-erosions, structures similar to cortical breaks presented by osteophytes, will be excluded (22). Each of the erosions will be documented at baseline and 48 weeks. Assessment includes the palmar, ulnar, dorsal as well as the radial sides of MCP 2-4 heads investigating overall 322 2D HR-pQCT slices in the transversal, sagittal and coronal plane. Every erosion of each patient will be characterised by the maximal width and depth of the lesion in the axial, sagittal and coronal using the open source DICOM viewer Osirix V3.2 (Rosslyn, VA, USA).

Erosion volume

The volume of the erosions will be calculated according to the methodology published by Fouque-Aubert et al (6). The volume of erosions (using the entire volume of interest) will be determined by manually defining the ROI including the erosion (V1) or excluding it (V2). The volume of erosions will be then calculated as: Verosion= V1-V2; V =sum(A_i*0.082), where A1_i or A2_i is the area on slice i (mm²), including or excluding erosion, and 0.082 mm is the thickness of slice (Figure 2).

Osteosclerosis

The signs of bone apposition at the margin of the erosion will be documented (8, 9). Semi-quantitative scoring (0-2 scale) of osteosclerosis will be performed using coronal reconstructions as follows: grade 0 = 0%, grade 1 = 1.75%, grade 2 = 75.100% bone apposition along the surrounding bone (typical images were shown in Figure 3) (23). Quantitative osteosclerosis will also be calculated by choosing the area (width =15 vexols) around bone erosion in MCP2-4 as ROI (24). The density of the ROI will be calculated as the mean pixel attenuation of that area. 3D registration will be applied to obtain a consistent segmentation of the periosteal surface in the vicinity of the cortical break, which is highly important for accurate quantification of bone damage.

Defining the healing of erosion

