This is the first study assessing erosion healing using HR-pQCT. Erosion healing is evidenced by a decrease in erosion volume and the presence of bone apposition at the margin of the erosion. Based on our preliminary data, the smallest detectable change of erosion volume, which was calculated on

the basis of 29 individual erosions as suggested by Bruynesteyn et al. (25), was 0.4 mm³. Meanwhile, a grade 2 osteosclerosis means dramatic bone apposition at the erosion margin (>75%). Therefore, a decrease in erosion volume of \geq 0.4 mm³ from baseline, and the presence of grade 2 osteosclerosis at the surface of erosion at 24 or 48 weeks is considered as strong evidence of erosion healing.

Osteophytes

The maximal height of each osteophyte will be documented by assessing the maximal distance between the surface of the osteophyte and the original cortical bone surface using the open source DICOM viewer Osirix V3.2 (Rosslyn, VA, USA) (17). The change of the maximal height between baseline and 52 weeks will be calculated.

Images will be evaluated by two independent readers blinded to the clinical data. Based on the posthoc analysis of a 6-months open-label randomized-controlled trial conducted by us (26), intra-observer reproducibility was 0.987, 0.994, 0.982, and 0.983 for erosion width, depth, volume and quantitative osteosclerosis, respectively. Inter-observer reproducibility as determined by intraclass correlation coefficient was: 0.977, 0.979, 0.962, and 0.974 for erosion width, depth, volume and quantitative osteosclerosis, respectively. Inter-reader agreement for the assessment of detecting the presence or the grade of osteosclerosis was also high (Kappa: 0.81~0.91).

Joint Space Width analysis

Volumetric joint space will be quantified using an algorithm developed by consensus from the Study grouP for eXtreme Computed Tomography in Rheumatoid Arthritis (SPECTRA) [33]. The 3-D JSW including mean (JSW.Mean, mm), maximum (JSW.Max, mm), minimum (JSW.Min, mm), SD (JSW.SD, mm), asymmetry [defined as JSW.Asymm = ratio of JSW.Max/JSW.Min,] as well as volume (JSV, mm³) will be calculated. Cuts through the sagittal and coronal planes (2-dimensional) will be automatically generated for visualization. A rheumatologist with HR-pQCT expertise will review all joints and score for degree of luxation (none, subluxation, luxation) and bone-on-bone contact (yes, no).

Ultrasound assessment of synovitis, dactylitis, enthesitis and digital pulleys

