Data processing and analysis Statistical analyses will be performed using the Statistics Package for Social Sciences (SPSS). Data will be analysed in an intention-to-treat manner. Patients who discontinued treatment or violated treatment protocol will be excluded from analysis. Missing data are assumed missing at random and will be treated using a multiple Imputation method (30). Based on the pilot study and our previous experience, the missing data is estimated to be less than 5%. Descriptive statistics will be used for demographic and clinical variables included frequencies, means and standard deviations, median and interquartile range. T-test, Mann-Whitney U test and Chi-square test will be used to evaluate differences in baseline characteristics between secukinumab group and placebo group. Changes of the outcome measurements between groups will be tested using t-test, Mann-Whitney U test, repeated measures analysis of variance (ANOVA) or Chi-square test where appropriate. Multivariate linear or logistic regression will be used to explore the association between the use of secukinumab and outcome measurements adjusting for baseline characteristics. A 2-tailed probability value of p < 0.05 is considered statistically significant.

Reference

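### Patients are randomised but erosions and osteophytes are measured one by one, and the analysis section names neither the unit of analysis nor a method for several lesions in one patient

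*Combined protocol and SAP*

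**What the plan says.** - **Randomised unit.** Under Plan of Investigation, Subjects: "The first 40 patients with erosion will be randomised in a 1:1 ratio to secukinumab (n=20) or placebo (n=20) group".
- **Primary outcome.** Under Objectives: "Difference in changes in the volume of erosions on metacarpophalangeal joints (MCP) 2-4 measured by HR-pQCT", at 24 and 48 weeks. It does not say whether volume is summed over a patient's erosions or taken erosion by erosion.
- **Healing outcome.** The first secondary outcome is "The percentage of erosions with healing determined using HR-pQCT on MCP 2-4 at 24 and 48 weeks". The section Defining the healing of erosion applies the definition to a single erosion: a volume decrease of at least 0.4 mm³, and "the presence of grade 2 osteosclerosis at the surface of erosion at 24 or 48 weeks is considered as strong evidence of erosion healing".
- **Level of measurement.** In the section on erosion identification, "Assessment includes the palmar, ulnar, dorsal as well as the radial sides of MCP 2-4 heads" and "Every erosion of each patient will be characterised by the maximal width and depth of the lesion". Under Osteophytes, "The maximal height of each osteophyte will be documented by assessing the maximal distance".
- **Analysis.** Data processing and analysis lists the t-test, the Mann-Whitney U test, "repeated measures analysis of variance (ANOVA) or Chi-square test where appropriate", and linear or logistic regression adjusted for baseline characteristics. The significance level is two-sided 0.05. The section names no unit of analysis, no rule for combining lesions, and no random effect, GEE or robust variance.

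**The concern.** Erosions in one hand share the patient's disease activity, treatment response and background medication, so they are unlikely to be independent. Four sides of three metacarpal heads are searched, and entry requires an erosion without setting an upper limit, so a patient can contribute several lesions.

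For a yes/no outcome expressed as a percentage of erosions, the listed methods that fit directly are chi-square and logistic regression. Applied to an erosion-by-arm table, both count each erosion as an independent unit. The standard error is then too small, and healing on secukinumab could be claimed too easily. The same holds for erosion volume and width, osteosclerosis and osteophyte height if they are tested per lesion.

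For the primary outcome the problem is the missing definition. A patient total and a per-erosion change computed from the same scans can give different p-values, and nothing in the plan fixes the choice before the data are seen.

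**Working it through.** **1. Inputs from the documents.** 20 patients per arm; two-sided alpha 0.05; healing defined per erosion; every erosion and each osteophyte measured. Not given: erosions per patient (m), the ICC, the expected healing rate.

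**2. The plan's own figure.** 2 × (1 − Φ(1.96)) = 0.050. For an unadjusted lesion-level test, this is the true error only if the design effect is 1, that is, one lesion per patient or ICC = 0.

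**3. Formula otherwise.** Design effect DE = 1 + (E[m²]/E[m] − 1) × ICC. True error = 2 × (1 − Φ(1.96/√DE)).

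**4. Illustration at an assumed ICC of 0.3.**

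| Assumed erosions per patient | E[m²]/E[m] | DE | Type I error |
|---|---|---|---|
| One in every patient | 1 | 1.00 | 5.0% |
| One in 75%, two in 25% | 1.75/1.25 = 1.4 | 1 + 0.4 × 0.3 = 1.12 | 6.4% |
| Two in every patient | 4/2 = 2 | 1 + 1 × 0.3 = 1.30 | 8.6% |

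Over ICC 0.1 to 0.5 the formula gives 5.5% to 7.4% in the second row (DE 1.04 to 1.20) and 6.2% to 11.0% in the third (DE 1.10 to 1.50).

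**5. Simulation check.** No treatment effect, 20 patients per arm, 20,000 runs per cell, ICC 0.3, assumed healing rates of 20% and 30%. Chi-square on erosions rejected in 6.4–6.5% of runs when a quarter of patients had two erosions, and in 8.3–8.8% when all had two. A t-test on lesion-level continuous values gave 6.1–6.5% and 8.3–8.8%. A t-test on patient means or patient proportions healed stayed at 4.7–5.4% in every scenario.

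**6. Efficiency of an unweighted patient summary** against an optimally weighted analysis. With v = ICC + (1 − ICC)/m, efficiency = [1/E(1/v)]/E(v).

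- A quarter of patients with two erosions, ICC 0.1: v = 1 or 0.55, E(v) = 0.8875, E(1/v) = 1.2045, efficiency 94%. At ICC 0.3, 97%.
- One, two or three erosions in 50%, 30% and 20% of patients, ICC 0.1: v = 1, 0.55 or 0.40, E(v) = 0.745, E(1/v) = 1.5455, efficiency 87%. At ICC 0.3, 93%.

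**7. Do the listed methods already cover this?** Repeated measures ANOVA is named without a within-subject factor. It fits the repeated visits, and nothing describes it as handling a varying number of lesions per patient. The t-test and Mann-Whitney are valid here only if each patient first contributes one value, and the plan does not say so.

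**The case against.** The plan never says that lesions will be tested as independent observations. The analysis section speaks of patients, of intention to treat and of baseline characteristics, and it lists the t-test and Mann-Whitney for use where suitable. An analysis of each patient's own percentage healed would fit that text. Inflation needs three things that the documents do not establish: testing by lesion, more than one lesion in some patients, and positive correlation.

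The inflation may also be modest. The plan expects over a third of screened patients to have an MCP erosion. If counts were Poisson with one third affected (an assumption), λ = −ln(2/3) = 0.405, and patients with any erosion would average 0.405/(1/3) = 1.2. The error at ICC 0.3 would then be 6.4%. Greater variation between patients, or the higher sensitivity of HR-pQCT, would raise it.

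Both arguments stand as limits on the claim. A reader might infer that the trial will analyse erosions as if independent, or that its false-positive rate is well above 10%. The documents support neither: the first is not stated, and the second needs lesion counts or an ICC that they do not give. What the objection does not remove is the omission. The outcome is worded as a percentage of erosions, no unit is named, and no listed method has a term for lesions within a patient.

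**Conclusion.** The point holds as a gap in the specification with a conditional risk; it is not a demonstrated error. What is certain is that the unit of analysis and the handling of several lesions per patient are not stated for any HR-pQCT outcome. If the healing outcome is tested erosion by erosion, the type I error is above 5% as soon as some patients have several positively correlated erosions. The values of about 6.4% and 8.6% rest on an assumed ICC of 0.3 and assumed lesion counts, so only the direction is firm. With one erosion per patient there is no inflation.

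For the primary outcome the documents support only that its unit is undefined and could be settled after the data are seen. They do not support saying that its p-value will be wrong. The point should be fixed before unblinding, because it touches the primary and several secondary outcomes and costs little to repair.

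**What to change.** Add to Data processing and analysis:

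- **Primary outcome:** each patient's total erosion volume over MCP 2-4 at each visit. State whether new erosions count.
- **Healing and other lesion-level outcomes** (erosion volume and width, osteosclerosis, osteophyte height): prespecify one of two routes. (a) A GEE or mixed model clustered on patient, with a small-sample correction for 40 clusters; this keeps the lesion-level summary. (b) One summary per patient, such as the proportion of erosions healed or the mean change, compared by t-test or Mann-Whitney.
- **Osteophytes:** state whether new ones count.
- **Joint space volume:** apply the same rule if the three joints are analysed separately.

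No particular cut-point for the 0–2 osteosclerosis grade is needed.

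**Cost.** Wording only, with no new data; the tests in (b) are already listed. P-values will be somewhat larger where lesions are correlated. Route (b) loses some efficiency (87–97% retained in the scenarios shown). It also weights patients equally rather than erosions equally. If healing depends on how many erosions a patient has, that is a different quantity from the percentage of erosions healed, so the SAP should state the choice.

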Exclusion criteria are: 1) limited in ability to perform usual self-care, vocational, and avocational activities; 2) pregnancy; 3) previous therapy with biologic; 4) the presence of active inflammatory diseases other than PsA; 5) active infection in 2 weeks before randomization or a history of ongoing, chronic, or recurrent infections including tuberculosis; 6) history of hepatitis B & C; 7) history of malignant disease within the past 5 years (excluding basal cell carcinoma or actinic keratosis, in-situ cervical cancer, or non-invasive malignant colon polyps); 8) contraindications to secukinumab. The concomitant use of oral glucocorticoids (at a dose of \leq 10 mg per day of prednisone or its equivalent) and methotrexate (at a dose of \leq 25 mg per week) are permitted, provided that the dose will be stable.

The study will be approved by the Ethics Committee of the Chinese University of Hong Kong. Written informed consent will be obtained from all participants according to the Declaration of Helsinki and ICH-GCP guidelines.

Methods This is a 52-week, randomized, placebo-controlled, double-blind study. PsA patients will be randomised to either secukinumab or placebo group. All patients will be evaluated and treated according to the following protocol.

Study design

Treatment

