The patients will be randomly assigned to the secukinumab group or placebo group. Patients will be followed-up at weeks 2, 4 and then every 12 weeks until week 52. Patients will receive subcutaneous placebo or secukinumab 150 mg once a week from baseline for 4 weeks, and then once every 4 weeks from week 4 onwards. The study flow is shown in Figure 1. Changes in the baseline treatment, e.g. the dosage of conventional synthetic DMARDs (csDMARDs) including methotrexate, leflunomide, hydroxychloroquine, or sulfasalazine or the addition of a new csDMARD (individually or in combination), as well as changes in the dosage or the addition of steroids or nonsteroidal antiinflammatory drugs were allowed after week 12 if the patient cannot achieve minimal disease activity (MDA) (Table 1) (see appendix 1 for the treatment protocol). For patients who fulfil the criteria for biologic DMARDs (bDMARDs) (Appendix 2) and are willing to be started on bDMARDs, the code will be broken, and they can either pay out of pocket or can apply for the Samaritan Fund for financial assistance, provided they must household-based pass а financial assessment (http://www.ha.org.hk/visitor/ha visitor index.asp?Content ID=10048&Lang=ENG&Dimension=100). Patients who have started bDMARDs apart from secukinumab will be excluded from the efficacy assessment. Adverse effects will be recorded.

Evaluation of disease activity and severity

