All possible side effect of the biologic and synthetic DMARDs used the study will be explained to the participants by the research nurse and the treating physician. To monitor the possible side effect, complete blood count, liver function tests and renal function tests will be performed every visit. Chest X-rays will be obtained at baseline and at the end of the study. The treating physician records all nonserious and serious adverse events, all reports of drug exposure during pregnancy, and all reports of misuse and abuse of the Novartis drug, other medication errors and uses outside of what is foreseen in the protocol, if necessary, make treatment adjustments in accordance with the protocol. Serious adverse events are defined as any adverse reaction resulting in any of the following outcomes: a lifethreatening condition or death, a significant or permanent disability, a medically significant event, hospitalization or prolongation of hospitalization, a congenital abnormality, or a birth defect. All adverse events from this trial will be reported to local IRB and Health Authority by the investigator according per requirement as holder of certificate of clinical trial. Any SAEs, reports of drug exposure during pregnancy and reports of Study Drug misuse or abuse, including initial and follow up reports, arising from the Study in subjects exposed to the Study Drug, as soon as it becomes available, but in any event within fifteen (15) calendar days of becoming aware of such information, will be forwarded to Novartis by transmitting it to Novartis Patient Safety team.

Erosion assessment by HR-pQCT

Image acquisition

Metacarpal bone erosion will be assessed at MCP 2-4 of the more severely affected or the dominant hand if both hands are equally affected using a HR-pQCT system (XtremeCT II; Scanco Medical AG, Bruttisellen, Switzerland). This system enables the simultaneous acquisition of CT slices with an isotropic resolution (voxel size) of 82 μ m. HR-pQCT scanning will be performed by a single investigator who is blinded to all the clinical information of the patients. A single examination will be performed for

measurements of MCP 2-4. An anteroposterior scout view will be used to define the region of interest (ROI). The scan region will be 80 slices distal and 242 slices proximal of the upper margin of the head of MCP3. Scan time will be around 8 min per patient and scan (8). The scans will be performed at baseline, 24 and 48 weeks.

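### The exclusion of patients who stop treatment is not limited to efficacy, and the plan defines neither a safety population nor a rule for adverse events after the code break

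*Combined protocol and SAP*

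**What the plan says.** Four places in the combined protocol and SAP bear on this point.

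- **Plan of Investigation, Subjects.** "The first 40 patients with erosion will be randomised in a 1:1 ratio to secukinumab (n=20) or placebo (n=20) group".
- **Treatment.** A patient who meets the criteria for a biologic and wants one is unblinded: "the code will be broken, and they can either pay out of pocket or can apply for the Samaritan Fund for financial assistance". The text then continues: "Patients who have started bDMARDs apart from secukinumab will be excluded from the efficacy assessment. Adverse effects will be recorded". The exclusion concerns efficacy only. Its exception for secukinumab implies that a patient who starts that drug by this route stays in.
- **Safety Data Collection and Reporting.** "The treating physician records all nonserious and serious adverse events". Events also go to the ethics board and the health authority, and serious events to the drug company. This section covers recording and reporting and says nothing about analysis.
- **Data processing and analysis.** The analysis is said to be by intention to treat. The next sentence is "Patients who discontinued treatment or violated treatment protocol will be excluded from analysis". It carries no efficacy qualifier, and the section mentions neither a safety population, nor an adverse-event summary, nor a period over which events are attributed to an arm.

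**The concern.** Adverse events are collected in everyone, but the only exclusion rule in the analysis section is worded for all analysis. Anyone who tabulates adverse events by arm under that rule leaves out the patients whose events were troublesome enough to stop treatment. Discontinuation because of an adverse event is a basic safety result of a placebo-controlled trial, and this rule cannot produce it.

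The alternative is to keep such patients, and that leaves a second gap. A placebo patient may be unblinded and then start secukinumab while event recording continues. The plan does not say whether later events belong to the placebo arm, to secukinumab, or to a separate period.

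**Working it through.** The plan gives no adverse-event rate, discontinuation rate or switch rate, so it has no figure to reproduce. The stated inputs are 20 patients per arm (Subjects) and the follow-up (Methods): "This is a 52-week, randomized, placebo-controlled, double-blind study". Every other input below is an assumption, used only to show scale.

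**1. The exclusion applied literally to adverse events**

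Let *n* be the number randomised to an arm, *a* the number with any event, and *d* the number who stop because of an event (*d* ≤ *a*).

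- True rate of events leading to discontinuation: *d*/*n*. Rate after exclusion: 0/(*n* − *d*) = 0 for every *d*. This result needs no assumption about rates.
- One patient as a share of an arm: 1/20 = 5 percentage points.
- Any-event rate after exclusion: (*a* − *d*)/(*n* − *d*).

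With *n* = 20 and an assumed *a* = 8 (true rate 8/20 = 40.0%):

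| *d* | Calculation | Rate shown |
|---|---|---|
| 0 | 8/20 | 40.0% |
| 1 | 7/19 | 36.8% |
| 2 | 6/18 | 33.3% |
| 3 | 5/17 | 29.4% |
| 4 | 4/16 | 25.0% |

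**2. Direction of the between-arm bias**

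Take a true 8/20 in both arms, so the true difference is zero.

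- Two stop for an event on secukinumab and one on placebo: 33.3% v 36.8%. Secukinumab looks safer.
- One stops on secukinumab and two on placebo: 36.8% v 33.3%. Secukinumab looks less safe.
- Two placebo patients without an event stop for another reason, and none stop on secukinumab: placebo shows 8/18 = 44.4% against 40.0%.

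The direction therefore depends on how many stop in each arm and why. The documents do not give this.

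**3. Switchers kept in the placebo arm for the full 52 weeks**

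If *s* of 20 placebo patients start secukinumab at week *w*, open-label time is *s*(52 − *w*)/52 of 20 person-years.

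- *s* = 2, *w* = 24: 2 × 28/52 = 1.08 person-years, or 5.4% of 20.
- *s* = 6, *w* = 12: 6 × 40/52 = 4.62 person-years, or 23.1% of 20.

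Assume constant event rates of 0.5 per person-year on placebo and 1.0 on secukinumab (true ratio 2.0). The rate shown for placebo is (0.5 × time on placebo + 1.0 × open-label time)/20.

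- *s* = 2, *w* = 24: (0.5 × 18.92 + 1.0 × 1.08)/20 = 0.527; ratio shown 1.0/0.527 = 1.90.
- *s* = 6, *w* = 12: (0.5 × 15.38 + 1.0 × 4.62)/20 = 0.615; ratio shown 1.0/0.615 = 1.63.

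With the two rates exchanged (true ratio 0.5), the second case gives (1.0 × 15.38 + 0.5 × 4.62)/20 = 0.885 and a ratio of 0.5/0.885 = 0.57. The effect pulls the ratio towards 1 from either side, and it is zero if nobody switches or the two rates are equal.

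**4. Whether both problems can occur together**

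A placebo patient who leaves blinded treatment for secukinumab has arguably discontinued. Under the analysis section that patient is dropped and adds nothing to placebo. Under the Treatment section the patient stays and the attribution question arises. The two problems cannot both apply to the same switcher. Which one arises depends on which section governs, and the plan does not say.

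**The case against.** The strongest reply is that there is no safety comparison to distort. None of the listed primary, secondary or exploratory outcomes is a safety outcome, and the analysis section does not mention adverse events. That section also states intention to treat, and the Treatment section can be read as keeping excluded patients for safety. Events in patients who stop still reach the ethics board and the health authority.

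Much of this stands. The consequences are conditional: they follow if recorded events are summarised by arm under the exclusion as worded. The gap remains, because a placebo-controlled trial that records every event will have to present them, and the one exclusion written for analysis gives a wrong result when applied to them. Reporting individual events to authorities does not replace a summary by arm. The intention-to-treat statement does not settle the matter, because the next sentence contradicts it.

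Two stronger readings are tempting and are not supported.

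- *A reader might infer that the plan makes secukinumab look safer than it is.* For the exclusion, that needs more event-related stopping on secukinumab. For switchers, it needs a higher event rate on secukinumab. The documents give neither.
- *A reader might infer that the plan counts events on open-label secukinumab as placebo events.* It nowhere says so. The rule is missing.

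**Conclusion.** The point holds as a contradiction that should be reconciled, together with a missing rule. The exclusion in Data processing and analysis conflicts with the intention-to-treat statement before it. It also fits poorly with the Treatment and Safety sections, which continue adverse-event recording without any such exclusion.

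One result is certain under a literal application: events leading to discontinuation are 0 in both arms whatever happened, with 5 percentage points at stake per patient. The other figures are illustrations on assumed rates: a true 40.0% shown as 36.8% to 25.0% when one to four patients stop for an event, and 5.4% to 23.1% of placebo time spent on open-label drug. They show possible scale only, and no direction of bias is claimed.

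Appendices 1 and 2 are not in the text available for review. The Treatment section cites them for the treatment protocol and for biologic eligibility, not for analysis.

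**What to change.** In Data processing and analysis, limit the exclusion of patients who discontinued or violated the protocol to an efficacy analysis labelled per-protocol. Then add wording such as:

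> Adverse events will be summarised in all patients who received at least one injection; the efficacy exclusions do not apply. Events leading to discontinuation will be reported by randomised arm. Events will be reported by randomised arm up to the start of any non-randomised bDMARD, including secukinumab obtained after the code break. Later events will be shown separately, by randomised arm and drug actually received, so that none is dropped from either arm.

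The last sentence matters. If post-switch events were simply set aside, late events in patients randomised to secukinumab who move to another biologic would disappear from their arm.

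The cost is a few lines of text and one or two extra tables. The tables need the onset date of each event and the start date of any bDMARD. No treatment or visit changes. The wording should be settled before unblinding.
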